5.1 General Principle

All statistical analysis were done by using SAS 9.4 or updated version.

In general, continuous variables were descriptively summarized using number of subjects, mean, median, SD, minimum and maximum. Categorical variables and rank variables were descriptively summarized using the frequency and percentage under each category or rank. Unless otherwise specified, missing data were not included for the calculation of percentage.

The analytical method of this study was predominantly descriptive, without predetermined hypothesis test regarding the comparison of various observation periods.

5.1.1 Visit Window

Treatment day is defined as the number of days on which safety/efficacy assessments are performed relative to the initiation of study drug treatment. The day on which the study drug treatment is initiated will be recorded as Study Treatment Day 1. Treatment day will be calculated as follows:

- Treatment day = date of assessment – date of initiation of study drug treatment + 1 (assessment occurs after study drug treatment)
- Treatment day = date of assessment – date of initiation of study drug treatment (assessment occurs before study drug treatment).

Since there may be deviations from the visit schedule during the actual trial operation, visit windows were created based on the scheduled treatment day of the visits in order that these deviated data could also be included in the visits for pooled analysis. If multiple assessments fall into the same visit window, the assessment closest to the scheduled treatment day in the visit window will be used in the pooled analysis. If there are multiple assessments that are equally close to the scheduled treatment date, the latest assessment will be used in the pooled analysis. The table below defines the scheduled treatment days and the width of window for visits at different assessment endpoints:

(I) Safety assessment endpoints (vital signs, laboratory tests)

Scheduled visits	Visit labels in tables/lists	Scheduled treatment days	Visit window (days)
Screening/Baseline, Visit 1	Baseline	1	≤ 1
Visit 2	Week 4	29	2 - 57
Visit 3	Week 12	85	58 - 127
Visit 4	Week 24	169	128 - 211
Visit 5	Week 36	253	212 - 295
Visit 6	Week 48	337	296 - 379
....		
Visit n	Week 12* (n-2)	$12 * (n - 2) * 7 + 1$	$12 * (n - 2) * 7 + 1 - 41 - 12 * (n - 2) * 7 + 1 + 42$

(II) Tumor assessments (only for division of the analysis visits for summary of the diameters of target lesions)

Scheduled visits	Visit labels in tables/lists	Scheduled treatment days (Day)	Visit window (days)
Screening/Baseline, Visit 1	Baseline	1	≤ 1
Visit 3	Week 12	85	2 - 127
Visit 4	Week 24	169	128 - 211
Visit 5	Week 36	253	212 - 295
Visit 6	Week 48	337	296 - 379
....		
Visit n	Week 12* (n-2)	$12 * (n - 2) * 7 + 1$	$12 * (n - 2) * 7 + 1 - 41 - 12 * (n - 2) * 7 + 1 + 42$

5.2 Analysis Population

- Full Analysis Set (FAS): including all patients who received at least one study treatment. Patients will be analyzed according to the treatment they received. The FAS will be the primary population in the assessment of efficacy.
- Safety Analysis Set (SS): same as FAS. All safety analyses will be analyzed using the Safety Set.

5.3 Study Participants

5.3.1 Patient Distribution

All patients will be summarized according to the analysis datasets. The number and percentage of patients in the FAS and SAF will be summarized separately.

The number of patients undergoing treatment, and in the FAS, the number and percentages of patients who ended the treatment and who ended the treatment for different reasons, and the numbers and percentages of patients who ended the trial and who ended the trial for different reasons will be separately summarized. The total number of patients screened in each study site and the number of patients in the different analysis sets will also be summarized separately.

The disposition of all patients in the FAS set will be tabulated.

5.3.2 Protocol Violations

Protocol violations of patients in the FAS analysis set will be tabulated for analysis. In addition, major protocol violations will also be tabulated for analysis.

5.3.3 Demographic and Baseline Characteristics

Demographic characteristics and baseline characteristics will be summarized and tabulated based on the FAS.

The following demographic characteristics and baseline characteristics will be summarized and tabulated separately:

Demographic characteristics

- Age and age group (18 to < 65 years, \geq 65 years)
- Gender
- Height
- Weight
- Body mass index (weight (kg) / (height (cm) / 100)²)

Baseline disease characteristics

- Type according to histological diagnosis
- Tumor staging
- Duration of illness (years, time from initial diagnosis to start of study treatment): if the day is missing in the patient's initial diagnosis date (year and month known), it will be imputed using the median value of the dates in that month, i.e., it will be imputed as 15th if that month consists of 30 days, or as 16th if that month consists of 31 days; if the month and day are missing in the patient's initial diagnosis date (year known), it will be imputed with June 30 of that year.

In addition, the following baseline tumor lesion examinations will be summarized by means of contingency tables or descriptive statistics (number of cases, mean, median, standard deviation, minimum, and maximum) according to the distribution of data types:

- Total number of lesions, number of target lesions, and number of non-target lesions (1, 2, 3, 4, 5 and > 5)
- Number of organs affected (1, 2 and ≥ 3)
- Distribution of organs affected
- Type of lesion (only target lesion, both target lesions and non-target lesions)
- Diameter of target lesion (short diameter of the nodular lesion or the longest diameter of other target lesions)

5.3.4 Medical History

The medical history will be summarized and listed based on the FAS.

The medical history will be coded using the Medical dictionary for regulatory activities (MedDRA) 23.0 or the latest version of the coding dictionary before database lock. The number and percentage of patients with at least 1 history will be summarized by System Organ Class (SOC) (in alphabetical order) and Preferred Term (PT) (in descending frequency).

All medical history was tabulated by patient.

5.3.5 Concomitant medications

Combined medications will be summarized and listed based on the SAF.

Combined medications will be using the latest version of World Health Organization (WHO) dictionary and Anatomical Therapeutic Chemical (ATC) codes prior to database lock. Combined medications will be categorized into prior and concomitant medications based on whether they are used at the start of study treatment:

- Prior medications, refer to medications used only prior to study treatment (i.e., medications ended before the start of study treatment)
- Concomitant medications, refer to medications used concurrently during study treatment (i.e., medications received at or after the start of study treatment, or medications used prior to the start of study treatment and continued after the start of study treatment). If the time of a combined medication relative to the start of study treatment cannot be determined, it will be considered concomitant.

If the start date of a combined medication is missing, it will be imputed according to the following rules:

- Missing days only: if the year and month are the same as the first dose of study drug, the date of the first dose of study drug will be used, otherwise it will be imputed with the first day of that month
- Missing month and day: if the year is the same as the first dose of study drug, the date of the first dose of study drug will be used, otherwise it will be imputed as January 1
- If the year, month, and day are all missing, it will be imputed directly with the date of the first dose of study drug

If the end date of a combined medication is missing and it is unknown if the combined medication is still in use at the end of study treatment, it will be imputed according to the following rules:

- Missing days only: impute with the last day of the month
- Missing month and day: impute with December 31
- If the year, month, and day are all missing, it will be imputed with the date of the last dose of study drug

For concomitant medications, the number and percentage of patients using at least 1 dose will be summarized according to ATC 2nd level (in alphabetical order) and Preferred Term (in descending frequency). Concomitant medications will be listed. Prior medication was only tabulated.

5.4 Safety Analysis (Primary Analysis)

All safety analyses were based on SAF.

5.4.1 Drug administration

Duration of study treatment exposure, cumulative dose, dose intensity, and relative dose intensity were summarized descriptively. Where:

- Dose intensity (mg/day) = cumulative dose (mg) / duration of exposure (days), where duration of exposure (days) = time of last dose of Afinitor – time of first dose of Afinitor + 1.
- Relative dose intensity (%) = dose intensity / planned daily dose (10 mg/day) × 100%.

Patients with a certain duration of exposure (< 12 weeks, 12 - < 24 weeks, 24 - < 36 weeks, 36 - < 48 weeks, 48 - < 60 weeks, 60 - < 72 weeks, 72 - < 84 weeks, and ≥ 84 weeks) were summarized; patients with certain relative dose intensity (0 - < 50%, 50% - < 70%, 70% - < 90%, 90% - < 110%, and ≥ 110%) were summarized.

In addition, the number and percentage of patients with dose adjustments/dose interruptions (1 and ≥ 2) were summarized, and the reasons for dose adjustments were summarized by number and percentage of patients.

If the end date is missing, the following rules are used to impute:

- Missing days only: if the year and month are the same as the last visit, the date of the last visit will be used, otherwise it will be imputed with the last day of that month
- Missing month and day: if the year is the same as the last visit, the date and month of the last visit will be used, otherwise it will be imputed as December 31. If the imputed date is later than the withdrawal date, the end-of-medication date is adjusted to withdrawal date - 1 day.
- If all year, month and day are missing, it will be imputed directly with the date of the last visit

Drug administration was tabulated by patient.

5.4.2 Adverse events (AEs)

Adverse events (AEs) were coded according to the latest version of MedDRA prior to database lock.

If an outcome is missing and there is no outcome date, the outcome of that adverse event will be considered "ongoing". In the causality assessment between the investigational drug and the adverse event, if the result is missing or unknown, that AE will be assessed as "suspected to be related to the investigational drug". Other missing data will be treated as missing.

Adverse events were classified by onset time of AE relative to start time of study treatment as:

- Pre-treatment period: from day of patient's informed consent to the day before first dose of study medication;

- On-treatment period: from day of first dose of study medication to 30 days after last dose of study medication;
- Post-treatment period: starting from 30 + 1 days after last dose of study medication.

In addition to the overview of adverse events, only treatment-emergent adverse events were summarized by the number and percentage of patients with AEs. However, all AEs (including pre-treatment and post-treatment AEs) were tabulated with data indicating whether the AE occurred before or during or after the treatment period. For AE with missing dates, the available information should be used as much as possible when determining the period to which the AE belongs. If it is still impossible to distinguish, please refer to Table 1.

Table 1 Handling of missing adverse event onset date

Known date information	Missing date information	Case	Period belonging to
[None]	DDMMYYYY		Treatment period
DDMM	YYYY		Treatment period
YYYY	DDMM	If year < year of time of the first dose of the study drug	Pre-treatment
		If year \geq year of time of the first dose of the study drug and \leq year of time of the last dose of the study drug	Treatment period
		If year > year of time of the last dose of the study drug	Post-treatment
MMYYYY	Day	If year < year of time of the first dose of the study drug	Pre-treatment
		If year = year of time of the first dose of the study drug, and month < month of time of the first dose of the study drug	Pre-treatment
		If year = year of time of the first dose of the study drug and month \geq month of time of the first dose of the study drug	Treatment period
		If year > year of time of the first dose of the study drug and < year of time of the last dose of the study drug	Treatment period
		If year = year of time of the last dose of the study drug and month \leq month of time of the last dose of the study drug + 2	Treatment period
		If year > year of time of the last dose of the study drug	Post-treatment
		If year = year of time of the last dose of the study drug and month > month of time of the last dose of the study drug + 2	Post-treatment
DDYYYY	Month	If year < year of time of the first dose of the study drug	Pre-treatment
		If year \geq year of time of the first dose of the study drug and \leq year of time of the last dose of the study drug	Treatment period

Known date information	Missing date information	Case	Period belonging to
		If year > year of time of the last dose of the study drug	Post-treatment

Note: If the end date of the adverse event is prior to the first dose, the adverse event is a pre-treatment adverse event, even if the onset date of the adverse event is missing.

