Its relationship to the study treatment (Reasonable possibility that AE is related: No, Yes, investigational treatment, Yes, the study treatment (non-investigational), Yes, both and/or indistinguishable)
4. Action taken with respect to study or investigational treatment (none, dose adjusted, temporarily interrupted, permanently discontinued, unknown, not applicable)
5. Whether medication or therapy was given (no concomitant medication/non-drug therapy, concomitant medication/non-drug therapy)
6. Outcome (not recovered/not resolved, recovered/resolved, recovering/resolving, recovered/resolved with sequelae, fatal, unknown)
7. Whether it is serious, where a serious adverse event (SAE) is defined as in Section 8.2.1

If the event worsens the event should be reported a second time in the CRF noting the start date when the event worsens in toxicity. For grade 3 and 4 adverse events only, if improvement to a lower grade is determined a new entry for this event should be reported in the CRF noting the start date when the event improved from having been Grade 3 or Grade 4.

All adverse events should be treated appropriately. If a concomitant medication or non-drug therapy is given, this action should be recorded on the Adverse Event CRF.

Once an adverse event is detected, it should be followed until its resolution or until it is judged to be permanent, and assessment should be made at each visit (or more frequently, if necessary) of any changes in severity, the suspected relationship to the study treatment, the interventions required to treat it, and the outcome.

Progression of malignancy (including fatal outcomes), if documented by use of appropriate method (for example, as per RECIST criteria for solid tumors or as per Cheson's guidelines for hematological malignancies), should not be reported as a serious adverse event.

Adverse events separate from the progression of malignancy (example, deep vein thrombosis at the time of progression or hemoptysis concurrent with finding of disease progression) will be reported as per usual guidelines used for such events with proper attribution regarding relatedness to the drug.

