10.4.3 Handling of missing values/censoring/discontinuations

Missing safety data will simply be noted as missing on appropriate tables/listings.

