10.5.3.2 Adverse events (AEs)

Summary tables for adverse events (AEs) have to include only AEs that started or worsened during the on-treatment period, the ***treatment-emergent*** AEs. However, all safety data (including those from the pre and post-treatment periods) will be listed and those collected during the pre-treatment and post-treatment period are to be flagged.

The incidence of treatment-emergent adverse events (new or worsening from baseline) will be summarized by system organ class and or preferred term, severity (based on CTCAE grades), type of adverse event, relation to study treatment

Serious adverse events (SAE), non-serious adverse events and adverse events of special interest (AESI) during the on-treatment period will be tabulated

All death (on-treatment and post-treatment) will be summarized.

The adverse events of special interest (AESI) include the following categories

- Non-infectious pneumonitis
- Stomatitis/ oral mucositis
- Reactivation of hepatitis B virus
- Cardiac disorders: Cardiac failure; ejection fraction decreased

All AEs, deaths and serious adverse events (including those from the pre and post-treatment periods) will be listed and those collected during the pre-treatment and post-treatment period will be flagged

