5.4.2.1 Overview of adverse events

The overview of adverse events included the number and percentage of patients with the following AE (reported by all grades and Grade 3/4, respectively):

- All death events
- Treatment-emergent deaths (all grades only reported)
- Treatment-emergent AE
- AE suspected to be related to the study drug
- Treatment-emergent SAE
- SAE suspected to be related to the study drug
- AE leading to discontinuation of medication
- AE leading to discontinuation of medication, suspected to be related to the study drug
- Other significant treatment-emergent AE (AE leading to interruption or change in dose or frequency of Afinitor, AE requiring additional treatment)

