5.4.2.4.3 Other significant AE

Other significant AE included: AE leading to discontinuation of medication, AE leading to withdrawal from the trial, and AE leading to interruption or changes in dose or frequency of Afinitor.

The number and percentage of patients with following significant AE were tabulated and summarized separately by SOC (in alphabetical order) and PT (in descending order of incidence):

- AE leading to discontinuation of medication, regardless of whether related to the study drug or not
- AE leading to withdrawal, regardless of whether related to the study drug or not
- AE leading to interruption or changes in dose or frequency of Afinitor, regardless of whether related to the study drug or not

The number and percentage of patients with following significant AE were tabulated and summarized separately by PT (in descending order of incidence) and CTCAE grade (Grade 3/4):

- AE leading to discontinuation of medication, regardless of whether related to the study drug or not
- AE leading to withdrawal, regardless of whether related to the study drug or not
- AE leading to interruption or changes in dose or frequency of Afinitor, regardless of whether related to the study drug or not

A patient would be categorized and analyzed based on the most severe one if he/she experiences an AE of different severities for many times.

The number and percentage of patients with following significant AE were tabulated and summarized separately by SOC (in alphabetical order), PT (in descending order of incidence), and CTCAE grade (all grades):

- AE leading to discontinuation of medication, regardless of whether related to the study drug or not
- AE leading to withdrawal, regardless of whether related to the study drug or not
- AE leading to interruption or changes in dose or frequency of Afinitor, regardless of whether related to the study drug or not

A patient would be categorized and analyzed based on the most severe one if he/she experiences an AE of different severities for many times.

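### Missing causality is set to related in every treatment period, and the related rows of the AE overview carry no treatment-emergent limit, so a pre-dose AE can be counted there as drug-related

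*SAP*

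**What the plan says.** The incidence of AEs suspected to be related to Afinitor is one of the primary endpoints (protocol Table 3-1, SAP 2.3). AEs are recorded from informed consent (protocol 8.1.1), and screening may begin 28 days before dosing (protocol Table 7-1), so pre-dose AEs will be in the database.

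SAP 5.4.2 fills in absent causality: "if the result is missing or unknown, that AE will be assessed as" suspected to be related. It names no treatment period, and it treats other missing AE data as missing, apart from a rule for absent outcomes. The same section then fixes the scope of the summaries: "In addition to the overview of adverse events, only treatment-emergent adverse events were summarized by the number and percentage of patients with AEs".

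The overview in SAP 5.4.2.1 has nine rows. Four are labelled treatment-emergent: deaths, AEs, SAEs and other significant AEs. The other five are all deaths, "AE suspected to be related to the study drug", "SAE suspected to be related to the study drug", AEs leading to discontinuation, and related AEs leading to discontinuation.

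The protocol differs on both matters. Section 10.5.3.2: "Summary tables for adverse events (AEs) have to include only AEs that started or worsened during the on-treatment period". Section 10.4.3: "Missing safety data will simply be noted as missing on appropriate tables/listings". SAP section 7, which is the place for changes to the protocol's methods, says there are none.

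**The concern.** An event that began and ended before the first dose cannot have been caused by the drug. If its causality field is blank, the SAP nevertheless makes it related, and nothing in the wording of the related overview rows takes it out again. The overview is where most readers will look for the related-AE incidence. A count there that includes screening events could be too high, and it could differ from the detailed tables in the same report, leaving two incidences for one primary endpoint. The two departures from the protocol also touch the primary analysis without being declared.

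**Working it through.** The documents state no figure that can be reproduced here, so the check is to trace one record through the rules and then bound the effect.

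**Tracing a record.** Take a patient with an AE that starts and ends during screening, with causality left blank, who is then dosed.

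1. Period: pre-treatment, by onset date. If onset is missing but the end date precedes the first dose, the note to SAP Table 1 gives the same period.
2. Causality: set to related by SAP 5.4.2. The Table 1 note assigns a period only and does not undo this.
3. Overview row for related AEs: no period condition, so the patient counts.
4. Detailed related-AE tables (SAP 5.4.2.2): treatment-emergent only, so the patient does not count. The related-SAE tables (SAP 5.4.2.4.2) treat a serious event in the same way.
5. Protocol 10.5.3.2: the event should not be in an AE summary table. Protocol 10.4.3: its causality should be shown as missing.

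Steps 3 and 4 disagree, and steps 2 and 3 depart from step 5.

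**Size per patient.** Planned N is about 60 (protocol 10.8, SAP section 4). One extra patient adds 1/60 = 1.67 points, and two add 2/60 = 3.33 points. This applies only if the patient is not already in the row through another related event.

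**Expected size.** Let p be the share of patients with a pre-dose AE, m the share of those whose causality stays missing, and q the share already counted in the row. Treating these as independent, expected extra patients = 60 × p × m × (1 − q). The documents give neither p nor m. The assumed ranges are p = 5% to 30% and m = 2% to 20%. For q, the only guide is the phase III pNET study described in protocol 1.2.1.2, where stomatitis alone was reported as an adverse reaction in 53.9% of the everolimus arm. The share with any related event must be at least that.

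| q | Low: p = 5%, m = 2% | High: p = 30%, m = 20% |
|---|---|---|
| 0 | 60 × 0.05 × 0.02 = 0.06 patients (0.1 points) | 60 × 0.30 × 0.20 = 3.6 patients (6.0 points) |
| 53.9% | 0.06 × 0.461 = 0.03 patients (0.05 points) | 3.6 × 0.461 = 1.66 patients (2.8 points) |
| 90% | 0.06 × 0.1 = 0.006 patients (0.01 points) | 3.6 × 0.1 = 0.36 patients (0.6 points) |

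The q = 0 line is a ceiling and is not realistic for the all-grade related-AE row, where most patients will already be counted. The related-SAE row and the Grade 3/4 related counts have lower q, so each misclassified event is more likely to change them. Pre-dose serious or severe events should also be rarer there, so p is lower too.

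**With the fix.** AEs assigned to the pre-treatment period add no patients to the related rows through the causality rule.

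**The case against.** The best reply is that the missing label is shorthand. The sentence that sets the overview apart is awkward and can be read as merely adding tables to it. Some exception is needed in any case for the row on all deaths, because protocol 10.5.3.2 asks for on-treatment and post-treatment deaths. The related-AE row comes directly after the treatment-emergent AE row, and likewise for SAEs, so each may be meant as a subset. Protocol 10.4.2 sends the primary analysis to 10.5.3, which carries the on-treatment limit. Missing causality should also be rare: protocol 8.1.1 asks for it on every AE, and protocol 9.4 raises queries for missing values. Finally, setting missing causality to related is conservative for on-treatment events, and the rule is openly recorded in the SAP's version history.

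Most of this stands as an argument about size and intent. It does not settle the text: a programmer who follows the SAP would have no instruction to filter these rows, and section 7 remains inaccurate.

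Three stronger readings may tempt a reader, and the documents do not support them.

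- *The primary endpoint as a whole is inflated.* The detailed related-AE and related-SAE tables already exclude events classified as pre-treatment. The exposure is in certain overview rows.
- *A pre-dose Grade 3/4 AE that improves after day 1 becomes treatment-emergent.* Protocol 8.1.1 does say that "if improvement to a lower grade is determined a new entry for this event should be reported in the CRF noting the start date" of the improvement. But protocol 10.5.3.2 defines treatment-emergent as started or worsened on treatment, and an improvement is neither. The SAP, which classifies by onset time, does not repeat that definition and would be clearer if it did.
- *Other significant AE has two conflicting definitions.* SAP 5.4.2.4.3 reads "Other significant AE included: AE leading to discontinuation of medication, AE leading to withdrawal from the trial" and adds dose changes, while the overview row lists dose changes and AEs needing treatment. The overview row spells out its own content and discontinuation has its own overview rows, so this is a matter of labelling.

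**Conclusion.** The point holds as a conflict between stated rules. Read literally, the SAP lets a pre-dose AE with blank causality count as drug-related in the overview. This goes against protocol 10.5.3.2 and 10.4.3, is undeclared in SAP section 7, and may leave the overview at odds with the detailed tables.

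The consequence is possible, not certain. It needs a pre-dose AE, causality still missing after queries, and no other related event placing the patient in that row. The documents give no basis for saying how many patients will meet all three conditions. Under the assumed ranges, with q = 53.9% as a floor, the all-grade related-AE row would move by 0.05 to 2.8 points, and by less if q is higher. The effect is therefore probably small. It can only raise the related counts. The analysis is descriptive, so no test or error rate is affected. The correction is worth making because it concerns a primary endpoint and costs very little.

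**What to change.** - **SAP 5.4.2.1:** label the related-AE, related-SAE and both discontinuation rows treatment-emergent, meaning started or worsened on treatment. Leave the row for all deaths unrestricted.
- **SAP 5.4.2, causality rule:** apply it only to AEs assigned to the on-treatment or post-treatment period, using Table 1 when onset is missing, and footnote how many causalities were imputed. Tying the rule to the assigned period, and not to a known onset date, avoids leaving AEs without an onset date undefined.
- **SAP 5.4.2, period assignment:** state that it follows the protocol's started-or-worsened definition, so a CRF entry that records only the improvement of a pre-dose AE is not treatment-emergent.
- **SAP section 7:** list the departure from protocol 10.4.3.

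The cost is a few lines of SAP text and programming, and the related-AE count may come out slightly lower. No information is lost, because pre-treatment and post-treatment AEs are still listed with their period.
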